### 3. Rationale for Addendum

The following additions are being made to Protocol I6T-MC-AMAJ (AMAJ) for patients in Japan in order to conform with local requirements. This addendum is to be performed in Japan in addition to all procedures required by this protocol or any subsequent amendments to this protocol.

This addendum enables the inclusion of patients with generalized pustular psoriasis (GPP) and erythrodermic psoriasis (EP). These variants of psoriasis are relatively rare but can be more severe than chronic plaque psoriasis. GPP is characterized by multiple sterile pustules all over the body and may be accompanied by systemic symptoms including fever, chills, severe itching, dehydration, rapid pulse rate, exhaustion, anemia, weight loss, and muscle weakness. For this addendum, the eligibility criteria for GPP are set by the Japan Ministry of Health, Labour and Welfare (MHLW). EP is a particular inflammatory type of psoriasis that can affect the whole body. The reddening and shedding of the skin are often accompanied by severe itching and pain, heart rate increase, fluid loss, and fluctuating body temperature. For this addendum, the eligibility criteria for EP are based on the accepted current medical practice (Takigawa et al. 2010). Both psoriasis subtypes can sometimes be life-threatening without adequate treatment. The treatment options available for severe plaque psoriasis have been used in both subtypes, but often these subtypes are refractory to existing therapies. There are significant unmet medical needs for effective treatments for patients with GPP or EP.

Based on (1) postmarketing findings in Japanese patients with rheumatoid arthritis who were receiving anti-tumor necrosis factor (TNF) agents (Takeuchi et al. 2008; Koike et al. 2009), (2) recommendations set by the Japanese Dermatological Association for use of biologics in psoriasis (Ohtsuki et al. 2013), and (3) possible safety issues of Japanese patients with general autoimmune disease who received immunomodulators or immunosuppressants, the following additions are being made to Protocol AMAJ for patients in Japan:

- Chest radiography will be performed:
  - at Week 52
  - for subjects who discontinue the study early, if more than 12 weeks have elapsed since the previous study radiography was obtained. If medically indicated, this radiography may be performed even when 12 weeks have not elapsed since the previous study radiography
  - chest radiography may be performed at any time during the study, including the follow-up period, if medically necessary in the opinion of the investigator
- Added explicit exclusion criteria and discontinuation criteria for patients with pneumocystis pneumonia (PCP)
- Added testing of serum beta-D-glucan levels (Tasaka et al. 2007)

- Added testing of serum KL-6 levels
- Discontinuation criterion added to discontinue patients who have any positive hepatitis B deoxyribonucleic acid (HBV DNA) test at any time during the study
- Modified HBV DNA monitoring for patients who are positive for anti-hepatitis B core antibody (HBcAb+) and/or positive for anti-hepatitis B surface antibody (HBsAb+) at screening
- Exclusion criteria modified to permit the use of concomitant therapy for GPP and EP

All Japanese patients must participate in this addendum and must provide informed consent to the addendum.

## 4. Protocol Additions

The added underlined text or ~~striketrough~~ text in the following sections shows the changes applicable to patients participating in Study AMAJ in Japan. Additionally, a list of additional clinical laboratory tests is provided in [Attachment 1](#).

### 4.1. Section 2: Schedule of Activities

Section 2: Schedule of Activities

Procedure a	Screening Period	Baseline	Induction Period							Maintenance Period								
			V3	V4	V5	V6	V7	V8	V9	V 10	V 11	V 12	V 13	V 14	V 15	V 16	V 17	V 18
Visit Number	V1 b	V2	V3	V4	V5	V6	V7	V8	V9	V 10	V 11	V 12	V 13	V 14	V 15	V 16	V 17	V 18
Week	-4	0	1	2	3	4	8	12	16	20	24	28	32	36	40	44	48	52
Day with Visit Tolerance Interval	≤28 days from V2	1	8 ± 3	15 ± 3	22 ± 3	29 ± 3	57 ± 5	85 ± 5	113 ± 5	141 ± 5	169 ± 5	197 ± 5	225 ± 5	253 ± 5	281 ± 5	309 ± 5	337 ± 5	365 ± 5
Chest Radiography for TB Screening e	X e																	X
Investigator Completed Clinical Efficacy Scales																		
Assessment of dermal symptoms		X		X		X	X	X	X	X	X	X	X	X	X	X	X	X
Global improvement score				X		X	X	X	X	X	X	X	X	X	X	X	X	X
Laboratory Tests																		
HBV DNA testing n	X					X	X	X	X	X	X	X	X	X	X		X	
Beta-D-glucan*	X																	
KL-6**	X																	

## Section 2: Schedule of Activities

Procedure a	ETV s	Follow-up Period t	
		V801	V802
Visit Number		V801	V802
Week		LV+4W	LV+12W
Day with Visit Tolerance Interval		29 ± 5	85 ± 5
Chest Radiography for TB Screeninge	X		
Investigator Completed Clinical Efficacy Scales			
Assessment of dermal symptoms	X		
Global improvement score	X		
Laboratory Tests			
HBV DNA testing n	X	X	X

Abbreviations: DNA = deoxyribonucleic acid; ETV = early termination visit; HBcAb = anti-hepatitis B core antibody; HBsAb± = hepatitis B surface antibody positive; HBV = hepatitis B virus; IP = investigational product; LV = last study visit; PCP = pneumocystis pneumonia; TB = tuberculosis; V = visit; W = weeks.

- a All activities should be completed prior to any study dose administration unless otherwise stated.
- b Visit 1 procedures may be conducted over more than 1 day as long as all tasks are completed within the allowable visit tolerance (at least 3 days should be allowed for receipt of laboratory test results).
- e Chest radiography will be performed locally at screening unless it has been performed within 3 months before initial screening (provided the radiographs and/or formal report are available for the investigator's review). In addition, chest radiography will be performed at Week 52, or for subjects who discontinue the study early if more than 12 weeks have elapsed since the previous study radiography was obtained. This radiography may be performed within 12 weeks if medically indicated. In the opinion of the investigator, if evaluating chest radiography is medically necessary, the investigator may do so any time during the study, including the follow-up period. For additional details, see revised Section 9.4.5.3 in Section 4.7 of the addendum.
- n Any enrolled patient who is HBcAb+ and/or HBsAb+ will undergo periodic monitoring of HBV DNA with HBV DNA testing (JSH 2017) (see revised Section 9.4.5.4 in Section 4.7 of the addendum). Any patient with a positive HBV DNA test at any time must be discontinued from the study and receive appropriate follow-up medical care, including consideration for antiviral therapy. (Refer to revised Section 9.4.5.4 in Section 4.7 of the addendum for further information regarding the timing of discontinuation).
- s If a patient discontinues IP early, the patient will complete the ETV and then enter the Post-Treatment Follow-up Period (V801 + V802).
- t All patients who receive IP but do not participate in Study I6T-MC-AMAH must enter the Follow-up Period and complete V801 + V802.
- \* Beta-D-glucan is required at screening and, if an investigator believes it is warranted, at subsequent visits; a beta-D-glucan test may be included in the work up panel at any time during the study, including in the follow-up period. If the beta-D-glucan test is positive, PCP needs to be ruled out. If PCP is ruled out and the investigator deems the patient fit to continue, the patient may continue in the study. If a patient has a confirmed diagnosis of PCP during the study, the patient must discontinue the study.

\*\* KL-6 is required at screening and, if an investigator believes it is warranted, at subsequent visits; a KL-6 test may be included in the work-up panel at any time during the study, including in the follow-up period.

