##### **9.4.5.4. Hepatitis B Screening**

Patients who test HBsAg+, test HBcAb+ in conjunction with positive confirmatory HBV DNA test, or have positive HBV DNA test, regardless of HBsAb status, at screening will be excluded.

Any enrolled subject who is HBcAb+ and/or HBsAb+ will undergo periodic monitoring of HBV DNA per the Schedule of Activities (Section 2).

In addition to the above, any enrolled subject who is HBcAb+ and/or HBsAb+ and who experiences an elevated ALT or AST level  $>3 \times$  ULN must undergo HBV DNA testing. If the HBV DNA test is negative, the investigator should consult with the Lilly-designated medical monitor regarding further management of the patient.

If the result of the HBV DNA test is positive but below quantification study drug should be withheld and a repeat test done immediately. The Lilly-designated medical monitor should be contacted regarding study status of the patient. If the result of the HBV DNA test is DNA positive and quantifiable, the patient must be discontinued from the study and should receive appropriate follow-up medical care, including consideration for antiviral therapy. A specialist physician in the care of patients with hepatitis (for example, infectious disease or hepatologist subspecialists) should be consulted, and the patient should potentially be started on antiviral therapy prior to discontinuation of any immunosuppressant therapy (including study drug). Timing of discontinuation from the study treatment, the study, and of any immunosuppressant therapy (including study drug) needs to be based on the recommendations of the consulting specialist physician in conjunction with the investigator and medical guidelines/standard of care.

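### The Japan addendum gives two on-study rules for an HBV DNA result that is positive but below quantification: mandatory discontinuation in the rationale and footnote n, withhold, repeat and consult in Section 9.4.5.4

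*Protocol*

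**What the plan says.** Three places in the current addendum text deal with a positive HBV DNA test after enrolment.

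- **Section 3, Rationale for Addendum**, lists among the changes: "Discontinuation criterion added to discontinue patients who have any positive hepatitis B deoxyribonucleic acid (HBV DNA) test at any time during the study".
- **Section 4.1, Schedule of Activities, footnote n**: "Any patient with a positive HBV DNA test at any time must be discontinued from the study and receive appropriate follow-up medical care". It then refers the reader to revised Section 9.4.5.4 "for further information regarding the timing of discontinuation".
- **Section 4.7, revised Section 9.4.5.4**, splits positive results in two. Below quantification: "If the result of the HBV DNA test is positive but below quantification study drug should be withheld and a repeat test done immediately", followed by "The Lilly-designated medical monitor should be contacted regarding study status of the patient". Quantifiable: "If the result of the HBV DNA test is DNA positive and quantifiable, the patient must be discontinued from the study". A closing sentence bases the timing of any discontinuation on the consulting specialist's advice, together with the investigator and medical guidelines.

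On who is tested, Section 9.4.5.4 says: "Any enrolled subject who is HBcAb+ and/or HBsAb+ will undergo periodic monitoring of HBV DNA per the Schedule of Activities". It adds a test for such patients whose ALT or AST exceeds 3 times the upper limit of normal. The note to exclusion criterion [13] admits antibody-positive patients who are HBV DNA negative. On reach, the rationale says: "All Japanese patients must participate in this addendum".

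**The concern.** Neither the rationale nor footnote n mentions quantification, so on their wording a below-quantification positive ends study participation. Section 9.4.5.4 leaves the same patient's study status open. This is a contradiction about whether a mandatory safety stop applies, not a missing detail.

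What is at stake is consistent handling of patients at risk of hepatitis B reactivation. Two sites with the same laboratory result could each point to current text and reach different outcomes. It would also be unclear whether keeping such a patient in the study is a protocol deviation.

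**Working it through.** No sample size, power or error rate enters this point. The check is a comparison of the texts, followed by a count of the scheduled tests.

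**Step 1. Rule by result category**

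| On-study HBV DNA result | Rationale and footnote n | Section 9.4.5.4 | Agree? |
|---|---|---|---|
| Negative | no discontinuation rule | none; consult the monitor on management after a triggered test | yes |
| Positive, below quantification | discontinue from study | withhold drug, repeat, contact monitor; study status open | **no** |
| Positive, quantifiable | discontinue from study | discontinue from study | yes |

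The texts part in 1 of 3 categories.

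**Step 2. Does a cross-reference resolve it?** Footnote n cites Section 9.4.5.4 twice, once for monitoring and once for the timing of discontinuation. Neither reference hands over the decision whether to discontinue. The timing sentence in Section 9.4.5.4 follows the quantifiable branch and does not decide the below-quantification case. The addendum's addition to Section 8.2 (its Section 4.6) has a single bullet, on pneumocystis pneumonia, so it does not settle the matter.

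**Step 3. Which tests does the split in Section 9.4.5.4 cover?** The section mentions scheduled monitoring, then the ALT/AST-triggered test, and places the split directly after the triggered test. It can be read as covering all HBV DNA tests or the triggered ones only. The conflict exists on either reading, because footnote n applies at any time.

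**Step 4. Count of scheduled tests after screening** (Schedule of Activities, HBV DNA row)

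- V6 to V15 (Weeks 4, 8, 12, 16, 20, 24, 28, 32, 36, 40): 10
- V17 (Week 48): 1
- On-treatment total: 10 + 1 = 11
- Early termination visit, V801 and V802: 3 more

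The last three do not count towards the conflict. Under footnotes s and t, the early termination visit follows early stopping of study drug, and V801 and V802 belong to the post-treatment follow-up. There is nothing left to withhold at any of them.

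Wide reading: up to 11 scheduled tests per patient, plus triggered tests. Narrow reading: triggered tests only, which have no fixed time. These are opportunities for the conflict to arise, not expected events. The documents give no frequency for below-quantification results.

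**The case against.** The strongest reply is that the practical gap is small. Footnote n sends the reader to Section 9.4.5.4 twice, and anyone who follows either reference reaches the withhold, repeat and contact steps. A site working from Section 9.4.5.4 must withhold drug and contact the sponsor's monitor, so on neither text does dosing simply carry on. The rationale is a summary of changes, while Section 9.4.5.4 is the detailed procedure. A site that withholds, repeats, consults and then discontinues satisfies every text. This largely stands and lowers the severity. It does not remove the contradiction, because Section 9.4.5.4 does not require the last of those steps and footnote n does.

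Two further limits also stand. The addendum shows its changes by underline and strikethrough, and no mark-up is visible in Section 9.4.5.4 in the text available, so its wording should be confirmed. The main protocol was not supplied, and the Section 8.2 addition opens as a supplement to it. A reader might infer that the announced HBV DNA criterion was never put into Section 8.2. The documents do not support that, because main-protocol Section 8.2 may already hold one. Whatever it says, the three addendum texts still differ from one another.

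**Conclusion.** The inconsistency is real and confined to one result category. What is unsettled is whether discontinuation after a below-quantification positive is automatic or decided with the medical monitor while drug is withheld. It should be fixed as a clarification of a safety rule. Confidence is medium to high, held back only by the mark-up that cannot be seen in Section 9.4.5.4.

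Three stronger readings are tempting, and the documents do not support them:

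- That some patients would keep receiving drug after a positive test without review. Both rules interrupt dosing.
- That all Japanese patients are exposed to the conflict. All must join the addendum, but periodic HBV DNA monitoring covers only the antibody-positive patients, who entered HBV DNA negative.
- That the trial's statistical conclusions are affected. Nothing in the documents shows this.

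The size given, up to 11 on-treatment scheduled tests plus triggered tests, assumes that the split in Section 9.4.5.4 covers every HBV DNA test. If it covers triggered tests only, no scheduled test is affected through that section. It would then also be unstated whether a scheduled positive follows footnote n alone.

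**What to change.** Reconcile the rationale, footnote n and Section 9.4.5.4 to one on-study rule for a positive but below-quantification result. The sponsor's medical team should choose the rule; this review takes no view on which is right. The reconciled text should state whether it covers scheduled tests, ALT/AST-triggered tests or both.

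Before issuing it, check the marked-up original of Section 9.4.5.4 to confirm that its wording is current, and check the rule against Section 8.2 of the main protocol.

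The cost is a short addendum clarification and a letter to the Japanese sites. No new visits, tests or analyses are needed.

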## 4.2. Section 4: Objectives and Endpoints

Objectives in the main protocol are not applied to GPP and EP patients. Selected endpoints in the main protocol are applied to GPP and EP patients. The following objectives and endpoints are added to the study as exploratory objectives:

**Table AMAJ(1).1. Objectives and Endpoints**

Exploratory  To assess the efficacy of mirikizumab in patients with GPP.
	
GPP ONLY
 
Time course of response to treatment as measured by the following measures:
 
 
• global improvement score
 
• assessment of dermal symptoms for GPP
 
• change from baseline in PASI
 
• change from baseline in DLQI total score
 
 
At Week 16 and Week 52:
 
 
• change from baseline in global improvement score
 
• change from baseline in assessment of dermal symptoms for GPP
 
• change from baseline in PASI
 
• change from baseline in DLQI total score
 

To assess the efficacy of mirikizumab in patients with EP
	
EP ONLY
 
Time course of response to treatment as measured by the following measures:
 
 
• global improvement score
 
• change from baseline in PASI
 
• change from baseline in DLQI total score
 
 
At Week 16 and Week 52:
 
 
• global improvement score
 
• change from baseline in PASI
 
• change from baseline in DLQI total score
 

Abbreviations: DLQI = Dermatology Life Quality Index; GPP = generalized pustular psoriasis; PASI = Psoriasis Area and Severity Index.

## 4.3. Section 5: Study Design

[figure not shown]
### 5.1. Overall Design

Study I6T-MC-AMAJ is a Phase 3 multicenter, randomized, double-blind, placebo- and active-controlled, parallel group, multi-period study in adult patients with moderate-to-severe plaque psoriasis. Approximately 1443 patients will be randomized to treatment groups involving

different mirikizumab doses, placebo, or secukinumab. The study is comprised of 2 treatment periods (Induction, and Maintenance) which together lasts for up to 52 weeks, followed by a 12-week Post-Treatment Follow-Up period. The main protocol for Study AMAJ will enroll patients with plaque psoriasis (Cohort 1).

In parallel, the AMAJ(1) addendum will enroll Japanese patients who are diagnosed as GPP by the Japanese Dermatological Association or EP who have  $\geq 80\%$  body surface area (BSA) involvement (with inflammatory erythema) (Cohort 2). Approximately 8 patients with GPP and 8 patients with EP will be enrolled in Cohort 2 in Japan. During the Induction Period, GPP and EP patients will receive 250 mg mirikizumab subcutaneously (SC) at Weeks 0, 4, 8, and 12. During the Maintenance Period, starting at Week 16, GPP and EP patients will receive 250 mg mirikizumab every 8 weeks (Q8W) SC for up to a total of 52 weeks. Placebo control is not required for the GPP and EP patient arms because placebo-controlled studies are not ethical for patients with these severe conditions. The enrollment period of Cohort 2 will begin in parallel with the enrollment period of Cohort 1, but Cohort 2 enrollment may continue for a longer period of time if necessary to achieve the numbers planned for Cohort 2.

Figure AMAJ(1).1 illustrates the study design.

Abbreviations: EP = erythrodermic psoriasis; GPP = generalized pustular psoriasis;  
 LV = last study visit; miri = mirikizumab; Q4W = every 4 weeks; Q8W = every 8 weeks; V = visit; w = weeks; W = week.

\* Option to enter Study AMAH or to enter the Post-Treatment Follow-Up Period.

Note: At Week 0 (V2), patients will be randomized in a 4:4:4:1 ratio to one of the following induction and maintenance period treatments: a) 250 mg miri at Weeks 0, 4, 8, 12 followed by 250 mg miri SC Q8W starting at Week 16; b) 250 mg miri at Weeks 0, 4, 8, 12 followed by 125 mg miri Q8W starting at Week 16; c) 300 mg secukinumab at Weeks 0, 1, 2, 3, 4, followed by 300 mg secukinumab Q4W starting at Week 4; d) placebo at Weeks 0, 4, 8, 12, followed by 250 mg miri Q4W starting at Week 16 through Week 32 followed by Q8W thereafter. Patients will receive placebo to maintain the study blind across treatment groups. Dosing is via subcutaneous injection (SC) for all treatments in all periods.

At Week 0 (V2), patients with GPP/EP will be assigned to 250 mg miri at Weeks 0, 4, 8, 12, followed by 250 mg miri SC Q8W starting at Week 16. Dosing is via SC injection for all treatments in all periods.

**Figure AMAJ(1).1. Illustration of study design for Clinical Protocol I6T-MC-AMAJ addendum (1).**

## 4.4. Section 6: Study Population

### 6.1. Inclusion Criteria

#### Type of Patient and Disease Characteristics

- [1] Present with chronic plaque psoriasis based on an investigator confirmed diagnosis of chronic psoriasis vulgaris for at least 6 months prior to baseline and meet the following criteria:
- A. Plaque psoriasis involving  $\geq 10\%$  body surface area (BSA) and absolute PASI score  $\geq 12$  in affected skin at screening (Visit 1) and baseline (Visit 2), and
  - B. sPGA score of  $\geq 3$  at screening (Visit 1) and baseline (Visit 2).
- [2] Candidate for systemic therapy and/or phototherapy
- [36] GPP ONLY:  
Meet the criteria for GPP set by the MHLW at screening (Visit 1) and baseline (Week 0; Visit 2).
- [37] EP ONLY:  
Diagnosed to have BSA  $\geq 80\%$  involvement (with inflammatory erythema) at screening (Visit 1) and baseline (Week 0; Visit 2).

### 6.2. Exclusion Criteria

- [13] Have hepatitis B or test positive for hepatitis B virus (HBV) at screening, defined as:
- A. Positive for hepatitis B surface antigen (HBsAg+),  
OR
  - B. Positive for hepatitis B core antibody (HBcAb+) in conjunction with positive confirmatory HBV for HBV deoxyribonucleic acid (DNA) test,  
OR
  - C. ~~Positive HBV DNA, regardless of anti-hepatitis B surface antibody (HBsAb) status.~~ Positive for hepatitis B surface antibody (HBsAb+) and positive confirmatory for HBV DNA

Note: Patients who are HBcAb+ and/or HBsAb+ and HBV DNA negative may be enrolled in the study. Patients who meet these criteria at screening will be monitored during the study as detailed in revised protocol Section 9.4.5.4 (Section 4.7 of this addendum).

- [16] Have had serious, opportunistic (see Section 9.2.3 and Appendix 4), or chronic/recurring infection (including pneumocystis pneumonia [PCP]) within 3 months prior to screening. Examples include, but are not limited to, infections requiring IV antibiotics, hospitalization, or prolonged treatment.
- [23] Have any other skin conditions (excluding plaque psoriasis, pustular psoriasis, and erythrodermic psoriasis) that would affect interpretation of the results (including, but not limited to, scleroderma, eczema, drug-induced psoriasis, guttate psoriasis, ~~pustular psoriasis~~, parapsoriasis, or cutaneous manifestations of other autoimmune diseases such as systemic lupus erythematosus).

